## INTRODUCTION

Central venous catheters (CVCs), peripherally inserted central catheters (PICCs), and hemodialysis (HD) catheters, a necessity in health care, are vital in both inpatient and ambulatory care settings. In the United States, more than five million central venous access are inserted annually, playing a fundamental role within the complex treatment modalities in critical care, total parenteral nutrition (TPN), and renal replacement therapies. The significant role of central lines in critical care and hemodialysis is coupled with impending problems that must be prevented, recognized, and managed as catheter-associated complications considerably increase morbidity, mortality, and healthcare costs.

Central lines account for up to 15 million catheter-days per patient year in intensive care units (ICUs). From 2000 through 2009 there was a 15% increase in ICU beds from 67,579 to 77,809. In hemodialysis there was a 25% increase in the use of CVCs for dialysis access. This increasingly high prevalence is projected to continue its upward trend in the number of intensive care and end-stage renal disease (ESRD) patients. In 2013, newly diagnosed cases were 117,162 above the 662,000 established ESRD population. Clinical documentation within the electronic medical record (EMR) systems is at the core of every patient encounter. EMR offers a vast reservoir of coded data across continuums of care enabling systematically structured evaluation from which meaningful prognostication on the quality and cost of care delivered can be derived. And, as it is a fact that comprehensive care is communicated through the medical record, therefore, the importance of documentation cannot be overstressed. EMRs can be used to identify adherence and variation in practice, inconsistencies in quality of care, and value based clinical decision. Thus EMRs are valuable clinical tools.

Table -1 Catheter Definitions and Indications for Use

| Catheter Type  | Definition  | Indications for Use   |
|--|---|---|
| Central Venous Catheter - CVC                        | A tunneled cuffed inserted via the internal jugular, axillary veins and the tip of the catheter is advanced into the lower one-third of the superior vena cava (SVC) at the level of the cavoatrial junction (CAJ).     | 
 
Chemotherapy and bone marrow transplant (BMT)
 
Plasmapheresis and leukapheresis
 
Intravenous (IV) antibiotic and antifungal therapy
 
Total parenteral nutrition (TPN)
 
Pain management (rarely)
 
 |
|  | A nontunneled, noncuffed inserted percutaneously into femoral, subclavian, or internal jugular vein   | -Short tem use   |
| Hemodialysis Catheter - HD                           | A cuffed tunneled central venous catheter dialysis tunneled into the superior vena cava used exclusively for hemodialysis therapy   | 
 
Hemodialysis access for acute and chronic renal failure, and end-stage renal disease (ESRD).
 
   |
| Peripherally Inserted Central Venous Catheter - PICC | Peripherally inserted central venous catheter inserted in a large peripheral vein, such as the cephalic or basilic vein, and then advanced until the tip rests in the distal superior vena cava or cavoatrial junction. | 
 
IV therapy lasting several weeks up to 6 months. 
 
TPN
 
Antibiotics
 
Analgesics
 
Repeated Blood Transfusions
 
Chemotherapy
 
 
 
                    |

## BACKGROUND AND SIGNIFICANCE

Central lines have no absolute placement contraindications. They afford a readily available vascular pathway for life-sustaining intravenous fluids, nutrition and medications,

repeated laboratory tests, high-flow infusions, hemodialysis, and hemodynamic monitoring that cannot be precisely measured via non-invasive means. A major factor in the choice of a central access is the intended need. A non-tunneled catheter is the best option for short-term use (days to weeks), PICCs for intermediate use (weeks to months), and tunneled CVCs for long-term care (months to years). At times when vesicant and vasoactive medications are required to avoid local tissue injury or when needed for extracorporeal therapies, central access becomes the only viable alternative. Central lines are categorized as either inserted centrally or peripherally inserted. PICC has become increasingly popular because they are easy to insert, is considered cost-effective, and has been perceived to be safe in comparison to CVCs. PICCs, however, is not without complications. Some of these complications include catheter fracture, leakage, infection, superficial and deep vein thrombosis (DVT). As with all invasive procedures, catheter-use has high probabilities for complications. With more than five million catheters inserted annually, the vulnerability of CVCs to complications mandates a careful, structured investigation from the time of insertion, during dwell time, and at removal. Central venous catheters, now commonplace in critical care, hemodialysis, and long-term care setting, requires specialized knowledge in care, management, maintenance, and documentation. Practitioners, care providers, manufacturers, and regulatory agencies have long recognized that central lines are problem prone. Mechanical, thrombotic, and infectious complications remain the leading cause of catheter malfunction and failure. The hydrophobic surface of CVCs promotes adsorption of protein and cellular adhesions, making them susceptible to thrombotic occlusion and fibrin sheath formation in as early as twenty-four hours after placement. These building blocks eventually precipitate obstruction, a frequent complication of central lines.

Catheter occlusion occurs within one to two years in approximately 14% to 36%, which can be due to mechanical causes, precipitation of TPN, and low pH medications. Occlusions interrupt and delay patient care, a compromise that often leads to cancellation of life-sustaining therapies, ultimately contributing to mortality and higher overall costs. Occlusions do not just impede critical treatment; they also result in infectious complications due to the formation of complex biofilms of bacteria, viruses, and fungi, an eventuality that situates the supposedly beneficial catheter as the source of problematic bloodstream infections and hospital acquired complications (HAC). Blood stream infections can exacerbate a patients' condition, especially when the patient is immunocompromised, as biofilms are difficult to eradicate due to its high resistance to host defenses and antimicrobials. Catheter-related infection is a serious complication leading to sepsis, septic shock, and a mortality rate as high as 25%. By many analyses, the cost of infectious complications is significant as it increases morbidity, mortality, length of stay, and financial resources. The Centers for Disease Control and Prevention (CDC) approximates the added cost per infection to be at \$16,550 therefore independently escalating hospital length of stay and cost. As a result, catheter utility should be measured by the improvement in a patient's condition relative to its use. Identifying variability in catheter function and the inverse proportionality relative to cost is critical in the current value-based purchasing reimbursement environment. Compounding this issue of economics in catheter management, the Centers for Medicare and Medicare Services (CMS) no longer reimburses for hospital-acquired central line-associated blood stream infections (CLABSI), a never event.

The second highest occurring never event in healthcare is central venous catheter infection, a clearly identifiable, measurable, and preventable HAC. Catheter-related complications are not only detrimental to a good prognosis but is also unacceptable to care

providers, payers, and institutions. The importance of vigilant central line management is required because catheter-related complications adds additional financial burden on healthcare institutions. Estimates of per infection attributable never event cost is between \$34,508 and \$56,000, with a yearly cost ranging from \$296 million to \$2.3 billion.

The emergence of the concept of “big data” in the EMR system has revolutionized patient care delivery. A principle standard in electronic documentation is easy access to relevant information and transparency, as information is openly shared. The seminal work of L. L. Weed (1968), titled: “Medical Records That Guide and Teach,” stresses the importance of a highly organized medical record; and the significant role in quality care as it puts a system to the multiple problems that directly and indirectly affect a patient. Moreover, data must be analyzed to derive meaningful use and improve quality, safety, efficiency, and cost. A vital clinical information that enables the continuing development and delivery of quality health care; inaccuracies translate to inaccurate reports that can lead to adverse events. Electronic documentation affords data abstraction for the purpose of epidemiological analysis. Furthermore, as the healthcare moves from volume-based to value-based purchasing (VBP), Information Governance Principles for Healthcare (IGPHC) of 2014 provides a sound framework: accountability, transparency, integrity, protection, compliance, availability, retention, and disposition – allowing for a compliance to standards of information and technology in healthcare. A health institution must have a documentation environment that is conducive to both patient and care provider, i.e. ownership and transparency.

## **STUDY PURPOSE AND RATIONALE**

Translating good clinical practice and best evidence into the care and management of central lines poses many challenges. Several experts have identified the existing gap between

policy awareness and adherence among providers and clinicians. A comprehensive review of the literature from 2001 to 2015 found few studies describing and quantifying existing clinician variability in care and management of centrally and peripherally inserted catheters. Therapeutic interventions in 21st century healthcare is assumed to be based on evidence demonstrating a net beneficial effect that is without supporting data. CMS value based purchasing now demands stakeholders (i.e. purchasers, payers, providers, clinicians, patients, and policy makers) to change the measurement of healthcare quality from the historical practice of individual judgement based primarily on clinician credentials to metrics. The high prevalence of central lines mandates a paradigm shift from the standard perception of complications being “inevitable” to “unacceptable” thereby setting elimination as the goal versus the current benchmarking comparisons. Specific outcome metrics for central lines should be identified in individual organizations with specific performance metrics. Hospitals need to monitor clinician adherence to specified outcome metrics for CVCs, PICCs and HD catheters.

The aim of this study is to document clinicians variation in practice in comparison to standard guidelines by the Medical Center’s approved Evidence-based Practice (EBP) guidelines, policies, and procedures for CVCs, PICCs and HD catheters by way of a structured retrospective review of the EMR system. This study will assist in future translational research and to design a prospective study on CVCs, PICCs and HD catheters.

## **RESEARCH QUESTION**

1. What are the outcomes associated with management of CVCs, PICCs and HD catheters in adherence with hospital approved EBP guidelines for CVCs, PICCs and HD catheters?

2. What are the mechanical/technical, thrombotic, and other adverse outcomes (Heparin induced coagulopathy) associated with central venous catheters due to variation in insertion and management practices of CVCs, PICCs and HD catheters?

## **HYPOTHESIS**

There is no statistical significant difference between mechanical/technical, thrombotic, and other adverse outcomes associated with CVCs, PICCs and HD catheters due to variation in insertion and management practices and with adherence to hospital approved EBP guidelines for CVCs, PICCs and HD catheters.

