## **PRIMARY OBJECTIVE**

1. To explore the association between mechanical/technical, thrombotic, and other adverse outcomes associated with CVCs, PICCs and HD catheters due to variation in insertion and management practices and with adherence to hospital approved EBP guidelines for CVCs, PICCs and HD catheters.

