## **PRIMARY ENDPOINTS**

1. To document number of mechanical/technical, thrombotic, and other adverse outcomes associated with CVCs, PICCs and HD catheters in two groups:
  - 1a. Clinicians interventions and management in adherence with hospital approved EBP guidelines for CVCs, PICCs and HD catheters.
  - 1b. Clinicians interventions and management not in adherence with hospital approved EBP guidelines for CVCs, PICCs and HD catheters.

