**Table 3- PICCs Inserted in Critical Care Units**

| PICC | 2015 | 2016 |
|-------------|-------------|-------------|
| MICU        | 32          | 10          |
| CCU         | 60          | 32          |
| CSICU       | 56          | 68          |
| SICU        | 44          | 56          |

A convenience sample of three-hundred medical records will be reviewed for this study, one-hundred and seventy-five CVCs, seventy-five PICCs, and fifty HD catheters representing 25%, 45% and 10% respectively of the total number of catheters inserted in 2016.

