## **DATA ANALYSIS**

The summary of the demographic characteristics will be presented. Continuous variables will be summarized using mean (SD) or median (interquartile range) depending on whether or not the data follow the normal distribution. Categorical variables will be summarized by frequency (percentage). Correlational analysis will be performed utilizing Pearson Correlation. Comparison of continuous variables between any independent groups will be examined using two-sided T-test or two-sided Wilcoxon rank sum test, analysis of variance (ANOVA) or Kruskal-Wallis test followed by pairwise tests, as appropriate. Categorical variables will be

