## **CASCADE STUDY**

examined using Fisher's exact test or Pearson's Chi-square test, as appropriate.

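### The only hypothesis is one of no significant difference, and no effect estimate or confidence interval is planned for the adherent versus non-adherent comparison

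*Combined protocol and SAP*

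**What the plan says.** The Hypothesis section contains one statement: "There is no statistical significant difference between mechanical/technical, thrombotic, and other adverse outcomes associated with CVCs, PICCs and HD catheters", continuing to variation in practice and adherence to the hospital's guidelines. No alternative hypothesis, alpha, detectable difference or margin appears anywhere.

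The Primary Objective is exploratory: "To explore the association between mechanical/technical, thrombotic, and other adverse outcomes". The Primary Endpoints section then sets up the comparison: "To document number of mechanical/technical, thrombotic, and other adverse outcomes associated with CVCs, PICCs and HD catheters in two groups", one group managed in adherence with the guidelines and the other not. The expected size of each group is not given.

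Under Data Analysis, categorical variables are summarised by frequency and percentage, and are "examined using Fisher's exact test or Pearson's Chi-square test, as appropriate". Continuous variables get mean (SD) or median (interquartile range) and are "examined using two-sided T-test or two-sided Wilcoxon rank sum test", or by ANOVA or Kruskal-Wallis. Pearson correlation is also planned, without saying for which variables. No confidence interval is named for any comparison. For the adherence comparison of categorical outcomes, no risk difference, risk ratio or odds ratio is named.

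Under Sample Size: "A convenience sample of three-hundred medical records will be reviewed for this study", made up of "one-hundred and seventy-five CVCs, seventy-five PICCs, and fifty HD catheters representing 25%, 45% and 10% respectively" of the 2016 insertions. There is no power or precision statement.

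**The concern.** A conventional null hypothesis is a statement about the population, for instance that complication risk is the same in adherent and non-adherent lines. This one is about a test result. Taken literally, it comes true whenever p exceeds the threshold, whatever the real risks are. The planned output for a categorical complication is two percentages and a p-value, which does not show the reader how large a difference the data still allow.

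According to the Benefits section, the results are to be used in designing a prospective study. That needs an estimated difference and its uncertainty. If a non-significant p-value from 300 charts were taken at face value, the later study could be designed on the belief that adherence has no bearing on complications, when the data had only failed to settle the question.

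**Working it through.** **The plan's own figure.** There is no power calculation to reproduce. The chart total adds up: 175 + 75 + 50 = 300. It rests on shares of insertions, not on a difference to be detected or a precision to be reached.

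**Inputs.**
- From the documents: 300 charts; two groups; Fisher's exact or chi-square test; an occlusion rate of 14% to 36% (Background and Significance).
- Assumed: two-sided 5% (the plan states two-sidedness only for continuous comparisons and gives no alpha); the adherent/non-adherent split, varied from 30/270 to 270/30; and the two ends of the occlusion range as the rate in adherent lines. That range describes occlusion within one to two years, so it may not apply to ICU dwell times or to other complications.

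**Power.** Normal approximation with pooled variance under the null:
- s0 = √[p̄(1−p̄)(1/n1 + 1/n2)], where p̄ is the pooled rate
- s1 = √[p1(1−p1)/n1 + p2(1−p2)/n2]
- power = Φ[(|p2−p1| − 1.96·s0)/s1]

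For 14% versus 21% at 150/150: p̄ = 0.175, s0 = 0.04387, s1 = 0.04369. Then (0.07 − 0.0860)/0.04369 = −0.366, and Φ(−0.366) = 0.36.

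| Adherent / non-adherent | 14% vs 21% | 14% vs 28% | 36% vs 54% |
|---|---|---|---|
| 150 / 150 | 36% | 85% | 88% |
| 225 / 75 | 32% | 76% | 78% |
| 75 / 225 | 25% | 71% | 78% |
| 270 / 30 | 21% | 52% | 49% |
| 30 / 270 | 11% | 35% | 46% |

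A true 1.5-fold rise from 14% would thus be missed 64% of the time at an even split (1 − 0.36) and up to 89% of the time at 30/270 (1 − 0.11). A doubling from 14%, or a 1.5-fold rise from 36%, would usually be found at an even split.

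**Precision.** The 95% half-width for a risk difference, taking a common rate p, is 1.96·√[p(1−p)(1/n1 + 1/n2)]. At 14% it is ±7.9 points for 150/150 and ±13.1 for 30/270 or 270/30. At 36% it is ±10.9 and ±18.1.

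**What the missing interval would show.** Take 21/150 (14.0%) in adherent lines and 32/150 (21.3%) in non-adherent lines, an illustration and not a forecast.
- Fisher's exact test: p = 0.13.
- Risk difference: 0.2133 − 0.1400 = 0.0733. SE = √(0.14·0.86/150 + 0.2133·0.7867/150) = 0.0438. 95% CI = 0.0733 ± 1.96·0.0438, or −1.3 to 15.9 points.
- Odds ratio: (32·129)/(118·21) = 1.67. SE of the log = √(1/21 + 1/129 + 1/32 + 1/118) = 0.308. 95% CI 0.91 to 3.05.

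Under the plan as written, this result would appear as 14.0%, 21.3% and p = 0.13, which agrees with the stated hypothesis. The interval shows that a rise of nearly 16 points is not excluded.

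**The case against.** The best defence is that the hypothesis is an ordinary null, awkwardly worded, which the tests are there to reject. On that reading no equivalence margin is needed. The surrounding text supports it: the objective is to explore, Study Design calls the work descriptive and correlational, and Limitations warns that the non-experimental design restricts what can be said about adherence and catheter success. If event counts are reported with group totals, anyone can compute the intervals afterwards.

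Much of this stands, and it rules out three stronger readings.
- A reader might infer a rule that p>0.05 confirms no difference. The documents contain no such rule, and no alpha on which to base one.
- A reader might infer that only significance tests are planned. Descriptive summaries and Pearson correlation are planned too. What is missing is an effect estimate with an interval for the adherence comparison.
- A reader might infer that a null result is the likely outcome even if non-adherence does material harm. That holds for small effects, low event rates or very unequal splits. The 85% and 88% figures show that it is not general.

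The defence does not remove the gap. The Limitations section covers missing data, the single site and the design; it says nothing about low power or how to read non-significance. Intervals that readers could work out for themselves are not a planned analysis.

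**Conclusion.** The point holds as a reporting and wording gap. The sole hypothesis is phrased as a non-significant test result, and the primary adherent versus non-adherent comparison of categorical outcomes has no planned effect estimate or confidence interval. With 300 charts, power ranges from 11% to 36% for 14% versus 21% over the splits examined, and reaches 85% to 88% at an even split for the two larger differences. A non-significant p-value could therefore coexist with a large effect.

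The figures rest on assumed alpha, split and event rates, and on a background occlusion range that may not fit this population. The documents do not show that the investigators intend to read non-significance as proof that adherence is irrelevant, only that the plan leaves the reading open. For an exploratory chart review this is a free improvement and not a must-fix.

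**What to change.** 1. **Hypothesis.** Replace the statement with an estimation aim that matches the Primary Objective: to estimate the difference in complication risk between adherent and non-adherent lines. Alternatively, state a null and an alternative about population risks.
2. **Data Analysis.** For each adherence-complication comparison, require event counts and group totals, the risk difference and the odds ratio, each with a 95% confidence interval, alongside any p-value.
3. **Interpretation.** Add a sentence saying that p>0.05 will not be read as no association, and that conclusions will be drawn from the interval.

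The cost is a change of protocol wording and some additional output from the same data set. No new data or extra charts are needed.

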## **PRIMARY OBJECTIVE**

1. To explore the association between mechanical/technical, thrombotic, and other adverse outcomes associated with CVCs, PICCs and HD catheters due to variation in insertion and management practices and with adherence to hospital approved EBP guidelines for CVCs, PICCs and HD catheters.

## **PRIMARY ENDPOINTS**

1. To document number of mechanical/technical, thrombotic, and other adverse outcomes associated with CVCs, PICCs and HD catheters in two groups:
  - 1a. Clinicians interventions and management in adherence with hospital approved EBP guidelines for CVCs, PICCs and HD catheters.
  - 1b. Clinicians interventions and management not in adherence with hospital approved EBP guidelines for CVCs, PICCs and HD catheters.

### Catheter Insertion - See Appendix B

Clinician performing insertion identified

- o Number of attempts documented
- o Radiologic confirmation

- Confirmation of catheter placement and PICC location
- Under Floroscopy

Indication for catheter-need documented

- TPN
- Intravenous fluids
- High flow infusions
  - Type of product infused
- Repeated laboratory tests
- Hemodialysis
- Medications
  - Long-term Antibiotic therapy
  - Infusion of vesicants
- Hemodynamic monitoring

